 - **Inclusion/exclusion criteria:** The patient's usual care provider (primary care or endocrinologist) will be identified from the electronic medical record and via patient self-report. Providers will be invited to anonymously respond to the survey via an electronic communication (Inbox message, email, or letter with a URL link—in case of external provider).
- **Week 1, 2, 4, 8, and 12:**
 - **Patients NOT meeting targets:** At 1-2, 4, 8, and 12 weeks, the study team will:
 - Provide advice to the patient on basal insulin titration.
 - Counsel patient on therapeutic lifestyle changes
 - Provide a letter with a summary of the CGM interpretation and counseling provided to the patient as well as any additional advice to the usual diabetes care provider using a standardized template. The letter will include a copy of the Ambulatory Glucose Profile and the Glucose Overlay from the previous 14 days.
 - **Patients meeting targets:** a summary letter with Ambulatory Glucose Profile will be sent to usual care providers at weeks 1-2, 4, 8, and 12.
- **Week 8:** In preparation for transitioning patient to the extension phase of the study, the usual care provider will be sent instructions for prescribing the CGM device, including a pre-filled certificate of medical necessity, if applicable.

Follow-up Encounters: Patients will be contacted 1-2 weeks after discharge to confirm CGM use and address any concerns. If needed, this visit can be converted to in-person if additional supplies and/or training is needed. Thereafter, in-person visits are only required for the completion of A1c and patient reported outcomes surveys and other visits can be completed via telephone call. Dexcom supplies will be shipped directly to patients monthly or can be picked up by the patient. CGM data will be reviewed on Clarity and sent to the usual diabetes care provider after every visit as noted above. Diabetes medications and healthcare utilization will also be reviewed at each visit. At the 12 week visit, patients will complete patient-reported outcomes surveys and A1c.

Study Completion

Participants will receive an order to complete the A1c at 12 weeks via point-of care assay. They will be asked to complete additional surveys (Table 5). The study team will complete the 12 week visit and send a final communication to the healthcare provider with a summary of the visit, notice of study completion with study extension phase, the patient's Clarity sharecode, and CGM report.

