The database used for this study is REDCap, which is a secure web-based application for building and managing data. It is designed specifically for clinical research and administered by the OSU Center for Clinical and Translational Research. Permission for data access or entry will be granted or revoked at a level that is appropriate for each individual involved in the study. Following verification, data will be locked. Data and data labels can be downloaded selectively (for interim progress reports) or in entirety (end of study) directly from REDCap in SAS or Excel format.

Baseline Data:

- Demographics: gender, race/ethnicity, age, marital status, education, employment, insurance, marital status, contact information
- History: diabetes duration, tobacco use, microvascular/macrovascular complications, heart failure, conditions requiring anticoagulation (thromboembolism, atrial fibrillation), hypertension, hyperlipidemia, liver disease, hypoglycemia awareness, reason for hospital admission
- Medications: pre-admission, discharge, and follow-up insulin use and total daily dose, insulin type, other glucose-lowering medications, steroid use, anticoagulants, antiplatelets
- Exam: weight, height, BMI
- Surveys: MPSSS, eHEALS, SNS-3
- Labwork: eGFR, A1c, glucose level on admission and discharge
- Patient reported outcomes: DTSQs, DDS
- Additional patient questions about CGM use
- CGM target (Table 4)

Visit 1, 2, 3:

- Glucose data: detailed below
- Communication: to usual care provider (summary only, summary with advice)
- Diabetes medications, bolus insulin use, basal insulin dose, missed doses
- Adverse events (sensor irritation, infection, bleeding)
- Additional patient questions about CGM use
- Healthcare Utilization: PCP visit, education visit, endocrinology visit, hospital readmission, emergency visit
- CGM target (Table 4)

Visit 4:

- Glucose data: detailed below
- Communication: to usual care provider (summary only, summary with advice)
- Diabetes medications: non-insulin medication use by class, bolus insulin use, basal insulin dose, missed doses
- Adverse events (sensor irritation, infection, bleeding)
- Healthcare Utilization: PCP visit, education visit, endocrinology visit, hospital readmission, emergency visit
- Patient reported outcomes: DTSQs, DTSQc, DDS, BenCGM, BurCGM
- Additional patient questions about CGM use
- A1c
- CGM target (Table 4)

Visit 5, 6

- Glucose data: detailed below

Visit 7

- Glucose data: detailed below

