Usual Care Provider: usual care providers will complete a 12 item questionnaire which will include the 2 item provider type, years in practice, practice setting, specialty, % of patients with diabetes, familiarity with CGM, frequency of CGM interpretation, SUS-2 (ease of use, cumbersome to use), CGM report helpful in assessing glucose control, ambulatory glucose profile helpful for making adjustment in therapy, report recommendations helpful for making adjustments to therapy, whether Clarity website was accessed.

Potential Risks

There are no physical risks that would not otherwise be anticipated, as the blood draw for A1c is considered standard of care. No specific prescriptive regimen for medications is planned and therefore this also represents standard of care. Participants undergoing interstitial glucose monitoring, while considered a standard of care practice, may experience discomfort during sensor insertion, or difficulty with sensor adhesive such as irritation, pruritus, rash, or infection. In a study of the Dexcom G4, no device related serious adverse events occurred during the study (N=158).¹⁴ While the frequency of mild skin irritations with the Dexcom G6 have not been reported in a recent study,⁶³ mild reactions such as erythema, bruising, bleeding, infection have been reported with other devices, and may lead to device discontinuation.⁶⁴ Sensor accuracy may be affected by rapid changes in glucose, acute illness, theoretically resulting in over- or undertreatment of high or low glucose levels. However, studies have demonstrated that overall glucose control, including A1c, is improved and hypoglycemia risk is reduced. While the sensor is FDA approved for use up to 10 days, actual sensor life may vary. Psychological harm may be a possibility if participants neglect other aspects of self-care in favor of diabetes. However, this seems unlikely and will be averted with frequent contact and anticipated increased outpatient follow-up. No financial or legal consequences are anticipated. Breach of confidentiality is a possibility but with standard procedures for immediate entry of paper data into the secure online database, use of a study identification code on all data gathering instruments, and the use of electronic health records, this should be limited.

Usual Care Providers: the survey will pose limited risk, breach of confidentiality is very low as an anonymous electronic link will be provided.

Adequacy of Protection Against Risks

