kept in the office of the PI or the study coordinator and locked when not in use. Personal data that is otherwise not recorded into the database will be destroyed immediately through appropriate confidential shredding bins. After the program is complete and the data has been analyzed, all paper data will be shredded and electronic data will be de-identified after being stored for the minimum required amount of time. Personally identifiable past medical history and study data (glucose, laboratory assessments) will be obtained from EPIC, Redcap and the chart reviews. No highly sensitive information (mental illness, HIV status, social security number) will be collected and vulnerable populations such as prisoners will not be enrolled.

Study-related adverse events will be recorded and severe adverse events will be reported to the study PI and the institutional review board. Any severe adverse events felt to be related to the study will be reported immediately to the PI and IRB. Participants may leave the study for any reason and are assured that this will not otherwise affect their care. Thus, informed consent is treated as a continual process.

Usual Care Providers: We will use an anonymous electronic link. Moreover, we will not be collecting identifiers. The information requested is not sensitive information that would be expected to lead to psychological, professional, or physical harm.

Potential Benefits of the Proposed Research to Human Subjects and Others

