Participants may benefit from more intensive interaction with study staff, through improved glycemic control as well as close follow-up and anticipatory guidance. Benefits to society include improved glycemic control and hospital readmission, which may result in reduced medical costs, particularly among uninsured individuals. The risks are primarily related to breach of confidentiality and are limited, though still possible. Expert guidelines recommend glucose monitoring among insulin requiring patients using periodic finger stick glucose measurements or via continuous or semi-continuous interstitial measures (intermittently scanned glucose monitoring or CGM). CGM greatly reduces the need for fingerstick glucose monitoring and therefore minimizes discomfort related to glucose monitoring as it only needs to be replaced every 10 days. However, CGM is not widely adopted, primarily due to the expense. Moreover, CGM users have easy access to glucose values at any time and therefore are more likely to use the data to modify behaviors that affect glucose control. Thus patients may benefit from this technology as a result of participating in the study. Given the safeguards that are put in place, the potential benefits should outweigh the risks.

Usual Care Providers: Providers may obtain indirect benefit from additional support provided by the study in training patients to use CGM, assisting with obtaining and interpretation of reports, and improved glucose control among their patients.

Importance of the Knowledge to be Gained

The importance of the knowledge is in the understanding of the role of diabetes, in particular glucose control, on patient satisfaction outcomes in patients with cancer who were recently discharged from hospital. Currently, few studies have examined glucose control in this population following inpatient hospitalization. The rising epidemic of diabetes will continue to contribute significantly to the morbidity of these patients, frequently necessitating hospital care. Providing solutions to this problem is of considerable urgency. Therefore, the potential benefits outweigh the given the aforementioned risks.

REFERENCES

¹ American Diabetes Association. Economic Costs of Diabetes in the U.S. in 2017. *Diabetes Care*. 2018 May;41(5):917-928. doi: 10.2337/dc18-0007.

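### Study staff advise patients on insulin titration, but the risk text treats medication as standard of care, and a non-severe event after such advice may be left out of the adverse-event record

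*Combined protocol and SAP*

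**What the plan says.** **The intervention.** Communication with Usual Care Providers covers patients who miss their CGM targets. It begins "At 1-2, 4, 8, and 12 weeks, the study team will", and the first listed action is "Provide advice to the patient on basal insulin titration". A letter to the usual provider follows, summarizing the CGM interpretation and the counseling given.

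**The risk text.** Potential Risks opens with "There are no physical risks that would not otherwise be anticipated, as the blood draw for A1c is considered standard of care" and continues "No specific prescriptive regimen for medications is planned and therefore this also represents standard of care". Its only mention of treatment error concerns sensor accuracy under rapid glucose change or acute illness, "theoretically resulting in over- or undertreatment of high or low glucose levels". The section on potential benefits concludes: "The risks are primarily related to breach of confidentiality and are limited, though still possible".

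**The recording rule.** Protections against risk states: "Study-related adverse events will be recorded and severe adverse events will be reported to the study PI and the institutional review board". Immediate reporting is then required for severe events felt to be related to the study.

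**The data lists.** In Data Collection and Management and in section A.1.b, the adverse-event item for visits 1 to 4 and 7 gives three examples: sensor irritation, infection and bleeding. For communication at visits 1 to 4, the item is "Communication: to usual care provider (summary only, summary with advice", which describes what went to the provider.

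**The concern.** Advice on basal insulin titration, given by study staff on a study schedule and triggered by a study dashboard, is a study procedure even if nobody writes a fixed regimen. The plan treats its result as a program effect: change in basal insulin dose is an Aim 2 secondary endpoint, and decision support is part of the hypothesis. For risk purposes, however, medication is described as standard of care and the advice is not mentioned.

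That matters because of the order of operations in the recording rule. If only study-related events are recorded, relatedness has to be judged before an event enters the dataset, by staff whose protocol does not acknowledge the advice as a possible cause. The Work Plan foresees a poster and a first manuscript reporting efficacy and safety. With a single cohort there is no comparison group whose event rate could reveal under-recording. A low count of non-severe events could then partly reflect the filter.

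**Working it through.** No arithmetic applies. The plan states no figure on this point, and no sample size, power or alpha depends on it. The check sets the passages side by side.

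**1. Is the advice a study procedure?** Yes. The actor is the study team, the trigger is missing the Table 4 targets, and the times are weeks 1-2, 4, 8 and 12, so up to four contacts per patient. The Discharge paragraph leaves the discharge regimen and prescriptions to the primary team. That supports the statement about no prescriptive regimen at discharge, but it does not cover advice from study staff afterwards.

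**2. Is it named as a risk?** No. Potential Risks covers sensor insertion and adhesive, sensor accuracy, psychological harm and confidentiality. Over- or undertreatment appears only as a consequence of inaccurate readings. The benefits section says the risks are mainly confidentiality.

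**3. What can happen to an event after advice?**

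| Type of event or data | Where it is captured | Limit |
|---|---|---|
| Severe adverse event | Protections against risk: reported to PI and IRB | No relatedness limit in that clause; immediate reporting depends on judged relatedness |
| Non-severe clinical event | Protections against risk: recorded if study-related | Relatedness judged first; visit lists give only the three examples |
| Level 3 hypoglycemia | Aim 1 says it will be recorded | No field in either set of visit lists; absent from Endpoints |
| CGM time <70 and <54 mg/dl | Glucose data; Aim 1 secondary endpoints | A percentage of time, not an event record |
| Readmission, emergency visit | Healthcare utilization item | Collected whatever the cause; no cause field listed |

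The exposed row is the second, together with the missing field for level 3 events.

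**4. Do the schedule and the lists agree?** Not fully. Table 5 marks adverse events at visits 1 to 7 with no relatedness restriction. The written lists include an adverse-event item at visits 1 to 4 and 7, but at visits 5 and 6 they list glucose data only.

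**5. Can an event be related to advice?** Only indirectly. The per-visit items give the type of provider communication, the CGM target and the basal insulin dose. Patients are asked whether they changed basal insulin in the past 7 days in response to CGM data. The provider letter describes the counseling. No listed field says whether titration advice was given to the patient, in which direction, or when.

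**The case against.** The strongest reply is that standard of care does not mean unrelated in this protocol. The sentence after the one on medication also calls interstitial monitoring a standard-of-care practice, then lists its harms, and the visit lists record them. No passage defines study-related so as to exclude titration advice, so an investigator could class such an event as related. This stands: omission is possible under the wording but not required by it.

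A reader might also infer that the safety record will contain nothing beyond sensor-site reactions. The documents do not support that. Aim 1 promises level 3 hypoglycemia, the sensor measures low glucose, utilization is collected regardless of cause, Table 5 has an unrestricted adverse-event row, and the clause on reporting severe events carries no relatedness limit.

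A reader might further infer that events could never be traced to advice. That is too strong as well. The same trigger produces the advice to the patient and the provider letter, so a record of a summary with advice is a rough proxy. What remains is the lack of a direct field.

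Finally, the risk text denies a specific prescriptive regimen, which is narrower than denying any influence on medication, and the benefits section says primarily, which leaves room for other risks. Both points are fair. Neither supplies the missing acknowledgment of the advice.

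**Conclusion.** The point holds in a limited form. The intervention text and the risk text need to be reconciled. The recording rule and visit lists allow a non-severe clinical event after study advice to be judged unrelated and left out of the adverse-event record. Level 3 hypoglycemia is promised but has no listed field or endpoint. Other safety data are captured, without a direct link to advice given to the patient.

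The size cannot be given as a number of events. It is tempting to take the 60% that the Sample Size section anticipates will meet individualized TIR and treat the remaining 40% as receiving advice at every visit. That figure is stated without a visit, it is an expectation, and it would count advice contacts rather than unrecorded events.

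The conclusion assumes that the data lists reflect the forms to be built and that the recording sentence is applied as written. If the forms already log every adverse event, what remains is the inconsistent wording, the uncertain status of level 3 events and the missing advice field. No primary endpoint, analysis or sample size changes, and no view is taken on how insulin should be titrated.

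**What to change.** - Reconcile Communication with Usual Care Providers, Potential Risks, Protections against risk and the benefits section, so that titration advice is acknowledged as a study procedure and its risk is addressed.
- In Protections against risk and both sets of visit lists, record adverse events first, explicitly including level 3 hypoglycemia. Then judge relatedness to the device and to study advice as two separate items.
- Align the visit lists with the adverse-event row of Table 5, including visits 5 and 6.
- Add one field at each visit where advice can be given: titration advice given to the patient (yes/no, direction, date).

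The cost is protocol wording, a few REDCap fields and more events to log in a population with many comorbidities. Patient care does not change.
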